**Table 4: Sample size estimates to detect a range of plausible and ***clinically significant*** effect sizes**

	BP Effect Size	Non-HDL Effect Size
--	-----------------------	----------------------------

	5mmHg	6mmHg	7mmHg	10mg/dL	15mg/dL	20mg/dL
70% Power	278	190	140	248	110	64
80% Power	350	234	178	310	148	80
90% Power	466	340	232	424	184	104
Green cells represent sample sizes that are less than our proposed sample size (n=300).						

for each outcome. Three separate analyses for each outcome will be conducted to assess the effect of each potential moderator. Models will be fit in SAS PROC MIXED, as described above, and the moderating effect of each of the three factors will be assessed via the hypothesis test of the three-way interaction among subgroup, treatment, and time at 12 months.

**Analysis for Aim 3: The Process Evaluation:** Data will be analyzed by the Qualitative team in collaboration with PI. The analysis for this aim will use a mixed-methods approach. We describe these by outcome below.

**ASCVD Risk:** We will assess changes in the perceived ASCVD risk scale between intervention and control group using t-tests and will examine correlations between changes in perceived risk and changes in clinical outcomes.

Additionally, we will collect additional data on the context of the intervention by assessing changes in perceived ASCVD risk and care team networks. In a group of up to 27 participants, we will evaluate how perceptions of ASCVD risk qualitatively changed over the course of the intervention. As above, qualitative interviews with participants will be analyzed using standard thematic analytic techniques for qualitative data: identification of themes/domains, coding or classification of participants' responses by these themes performed independently by two team members; resolution of any coding discrepancies will be done by a third team member. To ensure consistency, a codebook and dictionary will be developed to create universal definitions for each code.

**Process Outcomes analysis:** The process evaluation will collect data on key implementation measures across the following six categories: **fidelity** (quality), **dose delivered** (completeness), **dose received** (exposure and satisfaction), **recruitment, reach** (participation rate), and **context**. Key measures of interest for each component of the intervention are described above under Aim 2 “Intervention components.”

**intervention relevant data:** (1) frequency of BP and lipid algorithm use; (2) number of telephone contacts and total duration of time required to bring an elevated BP or lipid level under control; (3) Frequency of statin intolerance and proportion of intolerance cases ending in complete cessation of any statin; (4) Number of referrals to BP or lipid specialists.

**Home BP monitoring relevant data:** (1) Frequency of home BP checks (average checks/week); (2) Number and nature of medication changes in response to home BP data.

**Support tools relevant data:** (1) number of times each tool is accessed; (2) proportion of subjects with missing data for NLA lipid targets tool.

**Exploratory Aim: If effective, [we will conduct a budget impact analysis] and simulate 10-year cost-effectiveness of the intervention.** Data will be analyzed by the Economic team ([name]) in collaboration with PI.

**Health economic analyses.** If the intervention is effective, we will conduct a budget impact analysis of the intervention costs at 12 months and simulate cost-effectiveness at 10 years. We plan to simulate 10-year rather than lifetime outcomes due to the lack of validated data for CVD outcomes past 10-years in an HIV cohort. We will apply a VA perspective in cost evaluation. To assess the cost-effectiveness of

the intervention, we will examine the difference in average health care and intervention costs between treatment and control arms (incremental cost), and difference in average effectiveness between treatment and control arms to calculate an incremental cost-effectiveness ratio (ICER) that summarizes the relative costs and benefits of the interventionist-led intervention.

**Budget impact analysis:** Fixed and marginal costs over the 12-month study period will be described using VA and study data. One-way sensitivity analyses will be used to demonstrate the impact of uncertainty in resource utilization. The unit cost will be multiplied by the estimated number of people potentially eligible for the intervention to project the budget required to scale the intervention.

**Cost effectiveness analysis:** Ten year ICERs are defined as the incremental cost divided by the difference in Quality-Adjusted Life Years (QALYs) to enable comparisons to other interventions under consideration for broader translation. To simulate 10-year outcomes, we will leverage the existing evidence on costs and utilities associated with hypertension control as well as competing risks and utilities specific to HIV populations with ART in high-income countries. The ACC/AHA pooled cohort equations for ASCVD risk will be applied to estimate 10 year ASCVD incident event rates. In the intervention scenario, we will apply relative risk ratios for ASCVD events associated with blood pressure-lowering therapies using the ACC/AHA systematic reviews informing the Million Hearts tool. We will use TreeAge to build a cohort-based simulation model, and apply parameter values that have been validated in prior cost-effectiveness studies. Costs for CVD preventative therapies will be extended out to the end of the period, applying published adherence/maintenance rates. Discount and inflation rates of 3% will be applied to out-year costs. One-way sensitivity analyses may be used to evaluate the impact of Reach and Maintenance on 10 year cost effectiveness. We will assess variability in the estimate using a probabilistic Monte Carlo sensitivity analysis with 1000 iterations and generate an acceptability curve presenting the percentage of simulation iterations for which the intervention achieves cost-effectiveness thresholds over a range of willingness-to-pay values.

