**Part 2: Intervention and Process Evaluation**

**Aim 2: Evaluate the 12-month efficacy of a intervention to improve systolic blood pressure in Veterans with HIV.**

We will conduct an RCT of our intervention vs. education control among HIV Veterans on suppressive ART who have hypertension. Education control participants will receive general prevention education. The primary outcome is change in systolic BP and the secondary outcome will be change in non-HDL cholesterol. As participants conclude participation in the RCT the Aim 3 Process Evaluation will be conducted with select intervention participants. Relevant information from aim 2 for the process evaluation is highlighted in yellow.

**Setting:** This trial will be conducted at the same sites described earlier: Durham VA, Baltimore VA, Cleveland VA, and Atlanta VA

**Participants:** We will enroll 300 HIV+ Veterans on suppressive ART and poor hypertension control ( $n=25-125$  at each site). Inclusion and exclusion criteria is listed in section 5.4. We will include individuals who have **hyperlipidemia**, defined as non-HDL > National Lipid Association (NLA) target or on lipid-lowering medication based on the last 3 years. While 300 is our enrollment goal, we may consent and randomize up to 310, to account for site differences, withdrawals and the scheduling availability and preferences of Veteran participants.

**Baseline visit:** Participants will attend an in-person visit during which the informed process will be completed (see section 5.3 for informed consent procedures). Once the veteran has provided consent and enrolled in the study, the baseline visit will also consist of:

- Have in-office BP obtained by a trained research assistant using a standardized protocol. If blood pressure is identified by study staff as being high (>180/110), similar to prior trials, we will provide feedback to both the patient and his/her primary care provider. In terms of the Veterans' provider, we will use a developed CPRS template (requiring co-signature) and/or phone calls to notify them. If no action is taken, the study physician at each respective site will follow up with the patients' provider.
- Measurement of vitals: height, weight, waist circumference
- Have blood drawn at VA lab to measure lipid panel. If lipid panel has been completed in the past 28 days, will not need to repeat during baseline visit.

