**Subsequent visits: (4,8,12 months)**

- Have in-office BP obtained by a trained research assistant using a standardized protocol mentioned above.
- Complete health-related surveys (see full list of measures in section 5.5). Surveys may also be administered by telephone or by mail if Veteran is unable to complete the research visit in-person, but priority will be given to in-person survey administration.
- Measurement of vitals: weight, waist circumference
- Have blood drawn at VA lab to measure lipid panel. If lipid panel has been completed in the past 28 days, will not need to repeat during follow-up visit.

**Randomization:** Study statisticians will develop a 1:1 blocked randomization scheme, stratified by site and hyperlipidemia status. The project coordinator and research assistant will be blinded to the randomization schema and will randomize each subject using an automated randomization methods embedded in the study tracking software. Participants will be randomized to one of two groups:

- Education control group
- Intervention

[figure not shown]
**Education control group:** Participants assigned to the education group at baseline will receive usual care enhanced with general prevention education delivered by the research assistant in person at lab collection times (0, 4, 8, and 12 months). Providers will not be able to see research outcome assessment of BPs since these are not placed into CPRS.

We believe it would be unethical to use a usual care comparison group. The Education control group is receiving more than usual care: education material given at each visit, BP monitored and documented in CPRS, and providers notified if BP exceeds safety thresholds, requiring their co-signature.

**Intervention:** Participants assigned to the intervention will also complete in-person visits every 4 months, as listed above but will also have additional contact with our interventionist who may be either a nurse or pharmacist. The in-person visits will be identical to those in the education control group, but without the in-person education material. At their baseline visit, individuals enrolled in the intervention will be invited to consent and enroll in the VA Annie program, allowing them to submit home BP readings via text message before their intervention contacts. This is an existing VA program, but will not be required to participate in the intervention.

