## 5.5 Study Evaluations

The table below lists which measures are collected from participants at each time point in the study. Data is recorded by the research assistant into secure study tracking SQL database or RedCap. The study team will develop an acceptable standardized time window for data collection around each timepoint.

Study visits/interactions:

Aim 1: Formative Evaluation

Qualitative Interview	x	
Adaptation Virtual meeting	x	
Revision Qualitative Interview	x	
Aim 2: Intervention	Intervention	Usual Care
Enrollment Visit (baseline measurements)	x	x
Intervention Call – 1 week after enrollment visit with Interventionist	x	
Follow-up Intervention Call – 2, 4, 6, 8, 10,12 month after first call with Interventionist	x	
Adhoc check in call/video visits for BP/Statin med adjustments	x	
4, 8, 12 month outcome measurements –in person visit* with RA (to include measuring height, weight, BP, waist, and lipid panel at lab)	x	x
Aim 3: Process Evaluation Feedback on the intervention collected by phone.	x	
Note: * if in-person study visits are discontinued for reasons out of our control or for pandemic closure we will convert them to VVC visits to capture BP outcome and schedule participants for labs with 4 weeks of BP collection. We will accept clinical labs for same lab if they have been collected within time frame.		

Patient surveys for each time point are attached at the end of this document.

Data element	Source(s)	Time period
Aim 1: Formative Evaluation		
Perceptions of the self-management for CVD, HIV. Lifestyle change and medication adherence.	Audio recordings and field notes from qualitative interviews	Aim 1:
Aim 2: Intervention/ Survey		
Chart Abstraction/Review and screening	Site CPRS medical records/CDW	Pre enrollment
Hypertension diagnosis	Site CPRS medical records/CDW	0, 12
HIV + diagnosis, HIV history (prior labs, treatment and appointments), recent hospitalizations and ED visits, MOVE program participation	Site CPRS medical records/CDW	0
Demographics, family history of CVD, health literacy, prior home BP use, technology use, life chaos, loneliness, pain, housing and food insecurity, financial strain, anxiety and depression, physical function	Self-reported survey responses	0
Medications, comorbidities, labs, alcohol use	Site CPRS medical records/CDW	0, 4, 8, 12
Health behaviors such as physical activity, diet, tobacco use, medication adherence, sleep, stress,	Self-reported survey responses	0, 12

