Data element	Source(s)	Time period
alcohol and substance use		
Aim 3: Qualitative Interviews		
Perceptions of CVD risk, self-management strategies and barriers, and intervention delivery strategy. For example, we will ask participants which aspects of the intervention were most and least helpful, appropriateness of the number and length of telephone sessions, and ways we may be able to further improve the intervention.	Audio recordings and field notes from semi-structured interviews	12
Optional sustainability interviews: 6-12 months after completing intervention, to hear participants' long-term perspectives from completing the study and developing a better understanding of the sustainability of the intervention	Audio recordings and field notes from semi-structured interviews	18 - 24 months
Exploratory Aim: Cost Impact Analysis		
Hospitalizations, Labor & Capital cost	CDW/Self-reported data	0, 12

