where  $Y_{ij}$  represents the outcome of interest (i.e., SBP or non-HDL) for patient  $i$  at time  $j$ . We will fit a common intercept and arm is the intervention group indicator. Similarly, time will be classified, where for example,  $I(month = 12)$  is a dummy variable equal to 1 for the 12 month time point. Random intercepts will be included for each individual to account for correlation among repeated measurements over time. The primary analytic model will adjust for clinic site and hyperlipidemia status. The mixed effects model parameters will be estimated and tested using SAS PROC MIXED (SAS Institute, Cary, NC), and the hypothesis of between-arm differences over time will be tested using estimate statements within PROC MIXED. In particular,  $\beta_7$ , the estimated difference in outcome between arms at 12 months, will be the primary effectiveness outcome

assessed. All analyses will be conducted following an intention to treat (ITT) principle.

**Missing data.** We will assess mechanisms for missing data in this study. LMM, implicitly accommodates missingness when the response is Missing At Random (MAR); that is, when missingness is due either to treatment, to prior outcome, or to other baseline covariates included in the LMM.

Our primary analysis will include all available study-collected data. A sensitivity analysis will be conducted by filling in missing data in the following manner:

1. Use all available study-reported data.
2. If missing study-reported value → use the SBP or non-HDL cholesterol value if available in the EMR in a 2 month window from the target data for that time point
3. If missing EMR-reported value → assess whether the outcome has >10% missing remaining.
  - a. If yes, ≥10% missing → use multiple imputation
  - b. If no, <10% missing → do not use multiple imputation, include only study- and EMR-reported values

The final determination whether to use multiple imputation is separate for SBP and non-HDL cholesterol outcomes; SBP could meet the criteria and non-HDL does not, or vice versa.

If multiple imputation is indicated, we will use multiple imputation procedures as described by Schafer. Once missing values have been imputed, each multiply-imputed data set can be analyzed using the LMM. Final parameter estimates and their standard errors will be calculated using Rubin's formula.

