**Power.** The power calculation for this study was based on our prior nurse-led BP intervention, a meta-analysis of lipid-lowering medication adherence interventions, and baseline BP and cholesterol data from our clinic sites. Power estimates were derived empirically via simulation in SAS 9.4. Simulated data were generated based on estimates from prior studies, such that we assumed a mean SBP at baseline of 145 mmHg for both arms, with a reduction in the education control arm of 1 mmHg by 12 months. For the intervention arm, we evaluated effect sizes (differences from education control at 12 months) of 5-7 mmHg. We estimate that 15% of patients may drop out by the 12-month time point, and incorporated missing values into the simulated data based on a uniform pattern of 5% missing at 4 months, 10% at 8 months, and 15% at 12 months. The drop-out rate is consistent with prior interventions at our sites (80-88% retention at 12 months). We conservatively estimated variance components assuming a total standard deviation of 17 and a within-individual correlation of 0.4 among repeated SBP measurements. Similarly, for the secondary non-HDL outcome, we assumed a baseline value of 132 mg/dL with a standard deviation of 41 and a within-individual correlation of 0.7, and evaluated sample size needed over effect sizes ranging from 10-20 mg/dL. After generating 1,000 simulated datasets under these assumptions, we fit the LMMs described above to each and assessed the effect of interest using two-sided tests with a type I error rate of 0.05. Based on results, we will have >80% power to detect a 6 mmHg lower systolic BP and >90% power to detect a 15 mg/dL lower non-HDL cholesterol in the intervention arm vs. education control. Table 4 displays the sample sizes needed to detect a range of plausible ***clinically significant*** BP and non-HDL effects. A 6 mmHg improvement in systolic BP is associated with a ~20% decrease in ASCVD events, and a 15 mg/dL improvement in cholesterol is associated with ~10% decrease in clinical ASCVD events.

Pre-specified sub-group analyses of the primary and secondary outcomes will include clinic site, sex, and baseline ASCVD risk category (10-20%, >20% or prior ASCVD). For each category, we will examine the interactions with intervention arm and time. Generally, the modeling approach will mirror that described above

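### The Aim 3 between-arm comparison of perceived ASCVD risk uses a change-score t-test that is valid but less precise than a baseline-adjusted analysis, and section 5.5 and the SAP do not list the scale for either trial arm

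*Protocol*

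**What the plan says.** Protocol section 5.6, in the ASCVD Risk paragraph of the Aim 3 analysis, states: "We will assess changes in the perceived ASCVD risk scale between intervention and control group using t-tests". The same sentence plans to correlate changes in perceived risk with changes in clinical outcomes. It names no instrument, covariates, time points or power.

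On design, section 5.1 (Randomization) states: "Study statisticians will develop a 1:1 blocked randomization scheme, stratified by site and hyperlipidemia status". For the Aim 2 outcomes, SBP and non-HDL cholesterol, section 5.6 fits a mixed model with a common intercept and states: "The primary analytic model will adjust for clinic site and hyperlipidemia status". A dated SAP update later removes hyperlipidemia from the non-HDL model.

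On measurement, section 5.5 introduces its schedule with "The table below lists which measures are collected from participants at each time point in the study", and the visit descriptions in section 5.1 refer to section 5.5 for the complete list of survey measures. Risk perception for trial participants appears there in one row, under Aim 3: "Perceptions of CVD risk, self-management strategies and barriers, and intervention delivery strategy". Its source is interview recordings and field notes, and its time is month 12.

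**The concern.** There are two separate issues.

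**Analysis.** A t-test on change subtracts the baseline score with a fixed coefficient of one and makes no use of site or hyperlipidemia. Regressing the 12-month score on baseline estimates that coefficient instead and, under randomization, is at least as precise in large samples. What is at stake is precision on one process measure.

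**Listing.** A between-arm comparison of change needs the same scale at baseline and follow-up in both arms. The only listed source for risk perception in the trial is qualitative, at month 12, and from a subset of intervention participants. As written, the analysis text and the measurement schedule do not match, and a reader cannot tell which scale is meant.

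**Working it through.** **Inputs from the documents.** Section 5.1: "We will enroll 300 HIV+ Veterans on suppressive ART and poor hypertension control". Section 5.6, Power: "We estimate that 15% of patients may drop out by the 12-month time point". Then 300 × 0.85 = 255 analysed, or 127.5 per arm. Tests are taken at the level stated for Aim 2, "two-sided tests with a type I error rate of 0.05". Strata: 4 sites × 2 hyperlipidemia levels = 8.

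**Inputs assumed.** Equal variance s² at months 0 and 12, and a baseline-to-12-month correlation ρ of 0.3 to 0.8. The protocol gives 0.4 for SBP and 0.7 for non-HDL, and nothing for this scale.

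**Plan's own figure.** None exists for this endpoint, so there is nothing to reproduce.

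**Precision.** Per-participant variance of the outcome analysed:

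- change score: 2(1 − ρ)s²
- baseline-adjusted: (1 − ρ²)s² = (1 − ρ)(1 + ρ)s²

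The adjusted variance divided by the change-score variance is (1 + ρ)/2, so the t-test needs 2/(1 + ρ) times the sample. The difference detectable with 80% power, in units of s, is (1.960 + 0.842) × √(2/127.5) = 0.351, multiplied by √(2(1 − ρ)) for change or √(1 − ρ²) for the adjusted analysis. At an effect where the adjusted analysis has 80% power, the t-test has power Φ(2.802 × √((1 + ρ)/2) − 1.960).

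| ρ | Variance ratio | Sample multiple for t-test | Detectable, change | Detectable, adjusted | t-test power when adjusted has 80% |
|---|---|---|---|---|---|
| 0.3 | 0.65 | 1.54 | 0.415 | 0.335 | 62% |
| 0.4 | 0.70 | 1.43 | 0.384 | 0.322 | 65% |
| 0.5 | 0.75 | 1.33 | 0.351 | 0.304 | 68% |
| 0.6 | 0.80 | 1.25 | 0.314 | 0.281 | 71% |
| 0.7 | 0.85 | 1.18 | 0.272 | 0.251 | 73% |
| 0.8 | 0.90 | 1.11 | 0.222 | 0.211 | 76% |

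**Strata.** Type I error of an unadjusted t-test on change was simulated with 8 strata of 32 participants, split equally between arms, and 8,000 replicates. It was 5.3%, 3.5% and 1.1% when the between-strata SD of change was 0, 0.5 and 1.0 times the within-stratum SD. Balanced allocation removes stratum differences from the arm contrast, but the t-test still counts them in its standard error. The test is therefore nominal to conservative.

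**Where the scale is listed.**

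| Place | What is shown |
|---|---|
| Section 5.5, Aim 2 baseline survey row | Itemised down to life chaos, loneliness and pain; no perceived-risk scale |
| Section 5.5, Aim 2 survey row for months 0 and 12 | Health behaviors; no perceived-risk scale |
| Section 5.5, Aim 3 row | Risk perception, qualitative, month 12 |
| Section 5.1, Aim 3 | Interviews with about 27–40 intervention participants |
| Section 5.1, Aim 1a | Names the Health Beliefs for Cardiovascular Disease Scale, for up to 18 formative-phase Veterans |
| SAP variable lists, models and table shells | No perceived-risk variable, although chaos and loneliness totals are listed |

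**The case against.** The strongest reply is that nothing here is invalid. A change score does take account of baseline by subtracting it, the t-test is unbiased under randomization, and omitting the strata does not inflate type I error. All of that stands. The measure is a contextual item in Aim 3, with no power claim attached. The common-intercept model is specified for SBP and non-HDL only, and the other process measures are simple counts, frequencies and proportions. A plain test here is therefore not a departure from how the plan treats everything else. The size of the gain also rests on an assumed correlation: at 0.8 it is only 11%.

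On measurement, a reader might infer from section 5.5 that the scale is not collected from controls, or that the comparison cannot be computed. The documents do not support that. Section 5.5 says that patient surveys for each time point are attached. Those forms are not in the text reviewed and may contain the scale. The health-behaviors row is also worded as examples by domain, not as a list of instruments. What remains is an inconsistency of listing and an unnamed instrument.

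**Conclusion.** The point holds as a minor one. The change-score t-test gives away precision without need: about 11% to 54% more participants for the same precision over ρ from 0.8 to 0.3, assuming equal variances at the two times. It is also conservative to the extent that site and hyperlipidemia predict the change. It is not biased.

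The measurement half holds as a mismatch between the analysis text and the lists in section 5.5 and the SAP. It does not show that data are missing.

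A reader might also take this as a threat to what the trial is designed to show, because low perceived risk features in the rationale. That goes too far. The protocol treats perceived risk as context in the process evaluation and says its influence on prevention behavior is poorly known. The SBP and non-HDL analyses do not depend on it.

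**What to change.** 1. Replace the t-test with a linear model of the 12-month score on arm, baseline score, site and hyperlipidemia status, or with the common-intercept mixed model used for SBP. Report the adjusted difference with its 95% confidence interval.
2. Name the instrument in section 5.6. List it in section 5.5 at months 0 and 12 for both arms, and add it to the SAP variable list or to a separate Aim 3 analysis plan.
3. Check the survey forms before settling the text. If controls were not measured, delete the between-arm test. If only the baseline score is missing, compare 12-month scores adjusted for site and hyperlipidemia, make no claim about change, and drop the planned correlation with change in perceived risk.

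The cost is a sentence or two of analysis text and one table row. No new data are needed if the scale is already on the survey forms. The fallback without a baseline score loses precision: leaving the strata aside, its variance is 1/(1 − ρ²) times that of the baseline-adjusted analysis, which is 1.10 at ρ = 0.3 and 1.33 at ρ = 0.5.

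### The 10-year cost model inflates and discounts the same future costs at 3%, so the discounting cancels, and no discount rate is given for QALYs

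*Protocol*

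**What the plan says.** The rule is in the Cost effectiveness analysis paragraph of protocol section 5.6: "Discount and inflation rates of 3% will be applied to out-year costs". The ratio itself is set out as follows: "Ten year ICERs are defined as the incremental cost divided by the difference in Quality-Adjusted Life Years (QALYs". No discount rate is attached to the denominator.

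The horizon is fixed in the Health economic analyses paragraph: "We plan to simulate 10-year rather than lifetime outcomes". Costs do run into the later years: "Costs for CVD preventative therapies will be extended out to the end of the period". The ICER's stated purpose is "to enable comparisons to other interventions under consideration for broader translation", and an acceptability curve over a range of willingness-to-pay values is planned.

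The work is conditional: "If the intervention is effective, we will conduct a budget impact analysis of the intervention costs at 12 months and simulate cost-effectiveness at 10 years". On one-way sensitivity for the 10-year model, the protocol says: "One-way sensitivity analyses may be used to evaluate the impact of Reach and Maintenance on 10 year cost effectiveness". Neither the discount rate nor the inflation rate is named there or in the description of the Monte Carlo analysis. No price year is given, and the 3% is not identified as real or nominal. The SAP lists the exploratory economic aim under Study Aims but contains no economic methods, so this protocol paragraph is the only specification.

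**The concern.** Discounting gives a dollar spent in year 10 less weight than a dollar spent now. Inflating that dollar at the same rate first removes the effect. An analyst who follows the sentence as written will report a discount rate of 3% while the constant-price costs carry a rate of 0%. The fault is therefore in a rule the plan states, and it would survive correct programming.

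The denominator adds a second problem. The only discounting sentence concerns costs, so one analyst could leave QALYs undiscounted and another could discount them at 3%, each believing the plan had been followed. The two would get different ICERs.

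At stake is the use the protocol gives for the ICER. Comparison with other interventions, or with willingness-to-pay values, needs a known price basis and a known rate on each side of the ratio. The 12-month budget impact analysis has no out-years, so this rule barely touches it.

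**Working it through.** The documents state no ICER, cost total or QALY total, so there is no figure to reproduce. The inputs from protocol section 5.6 are inflation i = 0.03, discount d = 0.03 and a horizon of 10 years. The time profiles below are assumptions, chosen to show the range.

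**1. Cancellation.** The factor on a year-t cost is ((1+i)/(1+d))^t = (1.03/1.03)^t = 1.000 for every t. With discounting alone, the year-10 factor is 1.03^−10 = 0.744.

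**2. Level cost stream, one unit a year for 10 years.** As written, the sum is 10.00. Discounted at 3% in constant prices:

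| Timing | Sum of 1.03^−t | As written / discounted |
|---|---|---|
| Start of year (t = 0–9) | 8.79 | 1.138 |
| Mid-year | 8.66 | 1.155 |
| End of year (t = 1–10) | 8.53 | 1.172 |

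Level costs are therefore weighted 14–17% more heavily.

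**3. QALY streams.** The discounted-to-undiscounted ratio for a level stream is 0.879 (start of year) or 0.853 (end of year). For gains rising linearly (weights k/55, k = 1 to 10), it is 0.840 (start of year) or 0.840/1.03 = 0.815 (end of year).

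**4. Effect on the ICER, with QALYs left undiscounted.** Let C0 and Q0 be undiscounted totals, and C3 and Q3 totals discounted at 3%. The ICER as written, divided by the ICER with both sides at 3% and no inflation, is R = (C0/C3) × (Q3/Q0).

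| Assumed profile | Calculation | R |
|---|---|---|
| Level costs, level QALYs | 1.138 × 0.879 | 1.00 |
| Level costs, rising QALYs | 1.138 × 0.840 | 0.96 |
| All cost at t = 0, level QALYs | 1 × 0.879 or 0.853 | 0.88 or 0.85 |
| All cost at t = 0, rising QALYs | 1 × 0.840 or 0.815 | 0.84 or 0.82 |

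Now suppose averted events bring savings totalling a fraction s of the up-front cost and rising linearly over the years (start-of-year timing). Then C0 = 1 − s and C3 = 1 − 0.840s:

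| s | C0/C3 | R, level QALYs | R, rising QALYs |
|---|---|---|---|
| 0.25 | 0.75/0.790 = 0.949 | 0.83 | 0.80 |
| 0.50 | 0.50/0.580 = 0.862 | 0.76 | 0.72 |
| 0.75 | 0.25/0.370 = 0.675 | 0.59 | 0.57 |

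**5. Effect on the ICER, with QALYs discounted at 3%.** Here R = C0/C3. Level costs give 1.14 to 1.17. Cost entirely at t = 0 gives 1.00.

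**The case against.** The strongest reply is that the numerator and denominator effects can offset. With QALYs undiscounted and both streams in the same time pattern, R is exactly 1.00, and the plan then returns the ICER that 3% on both sides would give. This stands, and it rules out saying that the rule always produces a distorted ICER. It does not make the rule safe. The model combines intervention cost, therapy cost carried to year 10 and benefit through averted events, and nothing in the plan makes those patterns match.

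A second reply is that 3% may be a nominal discount rate, for which inflating costs first is coherent. The procedure would be coherent, but the real rate would still be 0%. Under 3% inflation, a 3% real rate needs a nominal rate of 1.03 × 1.03 − 1 = 6.09%. Nor can the inflation term be read as bringing past prices up to date, because the sentence applies it to out-year costs.

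Third, a reader might infer that the plan has decided against discounting QALYs. The documents do not support that: they say nothing on QALY discounting in either direction, so the fair statement is that no rate is specified.

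Fourth, a reader might infer a fixed bias, for example an ICER about 15–18% too low. That needs costs concentrated at the start and year-end QALY weights, whereas the protocol runs therapy costs to the end of the period. The documents fix neither the size nor the direction.

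Finally, neither document calls the ICER a 3%-discounted figure or states the rate behind any comparator. How readers would take the result is a prediction.

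**Conclusion.** The cost rule is wrong as written. It names a 3% discount that has no effect in constant prices, and nothing in the SAP or the named sensitivity analyses would reveal or correct this. The cancellation is exact and needs no assumption. The 14–17% excess applies to a level 10-year cost stream, and its spread reflects only the timing convention.

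The consequence for the ICER is conditional. With QALYs undiscounted, the assumed profiles give ratios of 1.00 (both level), 0.96 (level costs, rising QALYs), 0.82–0.88 (up-front costs) and 0.83 down to 0.57 (up-front costs with later savings of 25–75%). With QALYs discounted at 3%, level costs give an ICER 14–17% too high. The missing QALY rate is a gap in the specification.

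The analysis is exploratory and is run only if the intervention is effective. The conclusions on systolic blood pressure and non-HDL cholesterol do not depend on it. The change is worth making before the model is run, but it is not critical to the trial.

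**What to change.** Replace the discounting sentence in the Cost effectiveness analysis paragraph with text such as:

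> Costs will be expressed in constant dollars of [stated base year], with no general inflation of future costs. Costs and QALYs will both be discounted at 3% per year. The discount rate will be varied in a one-way sensitivity analysis.

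A price index then has one role: bringing unit costs from earlier years to the base year. If the economic team prefers to work in nominal dollars, the plan should say so and give a nominal discount rate that includes inflation, together with the QALY rate.

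The cost is one sentence, a parameter change in the TreeAge model and one added sensitivity run. No trial data collection or clinical analysis changes. The ICER may move in either direction or not at all, depending on the time profiles.
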